6 CLINICAL PROCEDURES

6.1.1 Summary of procedures and follow-up

Day 0 Patient Recruitment, Informed Consent.

Pain Intensity (VAS), Lesion Measurement, Thermography, USS and Mouthwash Application

Day 7 Pain Intensity (VAS), Lesion Measurement, Thermography, USS, and Recording of Complications and Adverse Effects

Day 14 Pain Intensity (VAS), Lesion Measurement, Thermography, USS and Recording of Complications and Adverse Effects

6.1.2 Drop-out

All drop outs will need to be reported by recording the study group's reason for drop out. No included patient can be excluded from the final evaluation, for any reason, by the clinical investigators.

6.1 Evaluation of the primary objectives

- Pain intensity. It will be measured using the VAS consisting of a 10 cm line [13], where 0 indicates no pain and 10 indicates severe pain.
- Size of each ulcer. A sheet of transparent plastic will be applied directly to the ulcer and using a permanent waterproof marker the circumference of the ulcer has been traced and then placed on a graph paper counting them units of mm² included within the drawn area. Treatment will begin on the same day with strict infection control measures.

6.2 Evaluation of secondary objectives

- a. Thermography [16,17,19]
- b. Ulcer severity Score (USS) [18]:

Ulcer severity Score (USS)

	Characteristics of the lesion	Score	Description of the USS
Average number of injuries			Score = average number of ulcers in a culture Maximum score = 20
Average lesion size (in mm)			Score = mean size of ulcers in mm Maximum score = 20
Average duration of lesions (in weeks)			Score = number of 1/2 weeks i.e. Half a week (3 days) scores 1, one and

			a half weeks (10 days) scores 3. Maximum score = 10
Injury-free period (in weeks)			Score = 10 minus the average ulcer-free period in weeks Maximum score = 10 (never ulcer-free)
Patient-perceived pain (scaled from 0–10)			1 for slight discomfort in the presence of ulcers. ¹⁰ for excruciating ulcers that interfere with eating and speaking Maximum score = 10
Site of injury	Group 1 Labial mucosa Buccal mucosa Buccal sulcus Soft palate Belly of the tongue Floor of the mouth Group 2 Hard palate Adherent gum Alveolar ridge Dore of tongue Tonsils Tonsil pillars Uvula Oropharynx		Score = total of sites involved 1 for each site of group 1 (non-keratinized mucosa) 2 for each site of group 2 (keratinized, specialized) Maximum score = 10
Scarring	Yes/No		USS Total

Complications and adverse events: Any post-operative complications and adverse events (mucosal irritation, allergic reactions, etc.) will be recorded and reported by study group by blinded evaluators in the Complications, protocol deviation, and drop out.

7 ANALYSIS

7.1 Sample size

A sample size of 29 subjects for each group (power 80%) to detect a significant difference in means of 0.820 assuming the common standard deviation is 1.80 using a two-group t Student test with a significance level for $p<0.05$. Considering a 3% drop out, a sample of 30 subjects per study group will be enrolled.

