7.3 Statistical analysis

Descriptive statistics will be provided in summary tables by group based on the type of outcome measure summarized.

General descriptive statistics for continuous outcome measures will include n (number of observed values), mean with its 95% CI, standard deviation, median, minimum and maximum values. For categorical variables, the number and percentage of subjects with a specific level of the variable will be presented.

This primary efficacy analysis will be performed on ITT, using the null hypothesis of no between-group difference in overall VAS change from baseline between both groups:

$$H_0: \mu_{\text{AfteRapidDNA}} = \mu_{\text{Placebo}}$$

$$H_1: \mu_{\text{AfteRapidDNA}} \neq \mu_{\text{Placebo}}$$

Where μ is the mean change from baseline on Day 7 within the given product.

This hypothesis will be tested with an Analysis of Variance (ANOVA) with baseline values of VAS as a covariate. The groups will be compared to the bilateral significance level of 5%.

The assumption of normality will be verified by means of QQ graphs and by plotting the studentized residuals with respect to the expected values of the variable. If there are strong indications of non-normality of the data, the Wilcoxon Rank-Sum Test will be used to test the hypothesis of no median difference between buccacollutorio and placebo at Day 7 in a nonparametric manner. Summaries for each treatment group will include sample size, mean, median, standard deviation, minimum, maximum, Wilcoxon Rank-Sum test p-value, Hodges-Lehman point estimates of median treatment difference, and its 95% confidence interval.

From the Day 7 endpoint ANOVA model, a least squares estimate (LSMEANS) of the group effect and group difference (both with 95% confidence intervals) will be displayed along with the p-value of the difference between the groups.

Analysis will also be performed for the PP Analysis Set to test the robustness of the results.

For secondary quantitative efficacy variables, cross-treatment group comparison of change from baseline will be done by the same ANOVA model used in the primary efficacy analysis. Categorical derived variables (complications/adverse events) will be compared via a chi-square test or Fisher's exact test, as appropriate (chi-square test will be used if all groups have sufficient observations,

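### The stated inputs give about 40% power with 29 per group, not the 80% claimed in section 7.1

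*Combined protocol and SAP*

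**What the plan says.** Section 7.1 (Sample size) gives a target of 29 per group with 80% power to "detect a significant difference in means of 0.820 assuming the common standard deviation is 1.80 using a two-group t Student test", and continues "with a significance level for $p<0.05". It then allows for losses: "Considering a 3% drop out, a sample of 30 subjects per study group will be enrolled".

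Section 7.1 does not say whether the test is one- or two-sided. Section 7.3 (Statistical analysis) settles that for the primary comparison: "The groups will be compared to the bilateral significance level of 5"%. The same section compares VAS change from baseline at Day 7, with baseline VAS as a covariate.

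Section 7.1 names neither the outcome nor the day to which 0.820 and 1.80 apply, and it states no baseline-to-follow-up correlation.

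**The concern.** A difference of 0.820 against an SD of 1.80 is a little under half a standard deviation. Twenty-nine per group is far too few to detect an effect of that size with 80% power in a two-group t test, so at least one of the stated figures must be wrong.

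Section 7.1 is the only justification for the trial's size. If 0.820 and 1.80 are both right, the trial is more likely than not to miss the effect it names, and a null result would be reported as coming from a trial with 80% power when the true figure is about half that. If one figure is a misprint, the trial may be adequately sized, but the published rationale would still fail any reader's recalculation. Section 3 commits the trial to CONSORT reporting, so that rationale will be read.

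**Working it through.** **Inputs.** From 7.1: n = 29 per group, difference δ = 0.820, common SD σ = 1.80, two-group t test, 5% level, 80% power, 3% drop-out, equal groups. From 7.3: two-sided test.

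**1. Trying to reproduce 29.**
- Standardised effect: d = 0.820/1.80 = 0.456.
- Normal approximation: n = 2(1.960 + 0.842)² / d² = 75.6, so 76 per group.
- Noncentral t: n = 76.6, so 77 per group.

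The stated 29 is not reproduced.

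**2. Power at the stated size.**
- Standard error of the difference: 1.80 × √(2/29) = 0.473.
- Noncentrality: 0.820/0.473 = 1.73, against a critical t of 2.00 on 56 degrees of freedom.
- Power by noncentral t: 39.9% at 29 per group and 41.1% at 30. The normal approximation at 29 also gives 41.1%.

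**3. What 29 per group can detect.** At 80% power the detectable standardised effect is 0.7487. With σ = 1.80 that is 0.7487 × 1.80 = 1.35, and 1.35/0.820 = 1.64, so 64% larger than planned. With δ = 0.820 the SD would have to be 0.820/0.7487 = 1.095 or less.

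**4. Other readings of the inputs** (noncentral t, 80% power unless stated).

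| Reading | n required | Power at 29 |
|---|---|---|
| Two-group, one-sided 5% | 61 per group | 52.7% |
| One-sample or paired, two-sided | 40 | 65.9% |
| One-sample or paired, one-sided | 32 | 77.3% |
| Same, normal approximation | 30 (29.8) | – |
| 1.80 taken as a variance (SD 1.342) | 44 per group | 62.8% |
| 0.82 taken as a standardised effect | 25 per group | 86.6% |

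None gives 29. The one-sample readings also contradict the two-group test in 7.1, and the one-sided readings contradict 7.3.

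**5. Single changes that do give 29.**
- δ = 0.820 with SD 1.08: n = 28.2, so 29. The digits of 1.80 may have been transposed.
- SD 1.80 with δ = 1.35: n = 28.9, so 29. With δ = 1.36: n = 28.5, so 29.

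The document does not say which of these, if any, applies.

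**6. The baseline covariate in 7.3.** Let ρ be the correlation between baseline and follow-up VAS. The documents give no value, so the range is shown.
- If 1.80 is the SD of the follow-up score, the residual SD is 1.80 × √(1 − ρ²). Power at 29 is about 43%, 50% and 67% for ρ = 0.3, 0.5 and 0.7. Reaching 80% needs ρ of about 0.79.
- If 1.80 is the SD of change from baseline, with equal variances at both visits, the residual SD is 1.80 × √((1 + ρ)/2). Power at 29 is 67% at ρ = 0, 50% at 0.5 and 44% at 0.79. No non-negative correlation reaches 80%.

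**7. Drop-out step.** 29/0.97 = 29.9, so 30. This step is correct.

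**The case against.** The core arithmetic is not open to serious dispute, but there are fair objections to what is built on it.

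First, the primary analysis adjusts for baseline, so an unadjusted t test understates the power. That is true in direction, but 7.1 sizes the trial on a t test and states no correlation. Adjustment reaches 80% only if 1.80 is the SD of the follow-up score and the correlation is about 0.79 or more. Section 7.3 analyses change from baseline, and if 1.80 is the SD of change, power stays at or below 67% for any non-negative correlation.

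Second, the SD of 1.08 is conjecture. This stands: any SD from about 1.08 to 1.095 gives 29, and so does a difference of about 1.35 with the SD left at 1.80. The source of all three figures has to be checked, not only the SD.

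Third, if an input is only mistyped, the trial itself may have about 80% power. This also stands, so the prediction that the trial will probably miss its target effect depends on 0.820 and 1.80 both being the intended values. The statement in 7.1 is wrong in either case.

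**Conclusion.** The power claim in 7.1 is wrong as written. With a difference of 0.820, a common SD of 1.80, equal groups and a two-sided 5% two-group t test, 29 per group gives 39.9% power, against the 80% stated. The size that would deliver 80% is 77 per group. The result rests only on figures printed in 7.1 and on the two-sided level in 7.3. It does not depend on which outcome or day is meant, because the calculation uses only the ratio of difference to SD. Which input is in error cannot be determined from the document.

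**What to change.** Go back to the source of the difference, the SD and the sample size, and then revise 7.1.

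- If an input was mistyped, correct it and show that it gives 29. An SD of 1.08, for example, does.
- If 0.820 and 1.80 are both right, keep 30 per group and state the real properties, for example: *29 evaluable subjects per group give about 40% power for a difference of 0.82 and 80% power for a difference of about 1.35 (SD 1.80, two-sided 5% t test).* Add a reason why a difference of 1.35 would be worth detecting.
- In either case, name the outcome and day. Sections 4.4 and 6.1 list both pain VAS and ulcer size as primary, section 2 sets the hypothesis at 14 days, and 7.3 tests VAS at Day 7.
- If the covariate is relied on for power, state the assumed correlation, whether the SD is that of the follow-up score or of change, and the resulting power.

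The cost is one recalculation and a few lines in 7.1, with no extra patients. The price is a less favourable power statement unless an input was mistyped. If the sponsor prefers to keep 80% power for 0.820 at an SD of 1.80 by enlarging the trial, that needs 77 evaluable per group: 77/0.97 = 79.4, so 80 enrolled per group, or 160 in total against the present 60.

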7.2 Population

- **Intention-to-Treat population (ITT):** All randomized subjects who complete the clinical procedure and use mouthwash at least one day and with at least one available assessment of variables after baseline will be considered in this population.
- **Per-protocol population (PP):** All subjects in the ITT population with primary outcome measures available and without major protocol violations (e.g., misinclusions, poor compliance).

7.3 Statistical analysis

Descriptive statistics will be provided in summary tables by group based on the type of outcome measure summarized.

General descriptive statistics for continuous outcome measures will include n (number of observed values), mean with its 95% CI, standard deviation, median, minimum and maximum values. For categorical variables, the number and percentage of subjects with a specific level of the variable will be presented.

This primary efficacy analysis will be performed on ITT, using the null hypothesis of no between-group difference in overall VAS change from baseline between both groups:

$$H_0: \mu_{\text{AfteRapidDNA}} = \mu_{\text{Placebo}}$$

$$H_1: \mu_{\text{AfteRapidDNA}} \neq \mu_{\text{Placebo}}$$

Where μ is the mean change from baseline on Day 7 within the given product.

This hypothesis will be tested with an Analysis of Variance (ANOVA) with baseline values of VAS as a covariate. The groups will be compared to the bilateral significance level of 5%.

The assumption of normality will be verified by means of QQ graphs and by plotting the studentized residuals with respect to the expected values of the variable. If there are strong indications of non-normality of the data, the Wilcoxon Rank-Sum Test will be used to test the hypothesis of no median difference between buccacollutorio and placebo at Day 7 in a nonparametric manner. Summaries for each treatment group will include sample size, mean, median, standard deviation, minimum, maximum, Wilcoxon Rank-Sum test p-value, Hodges-Lehman point estimates of median treatment difference, and its 95% confidence interval.

From the Day 7 endpoint ANOVA model, a least squares estimate (LSMEANS) of the group effect and group difference (both with 95% confidence intervals) will be displayed along with the p-value of the difference between the groups.

Analysis will also be performed for the PP Analysis Set to test the robustness of the results.

For secondary quantitative efficacy variables, cross-treatment group comparison of change from baseline will be done by the same ANOVA model used in the primary efficacy analysis. Categorical derived variables (complications/adverse events) will be compared via a chi-square test or Fisher's exact test, as appropriate (chi-square test will be used if all groups have sufficient observations,

otherwise Fisher's exact test will be used). All statistical comparisons will be conducted at the significance level 0.05. SAS version 9.4 will be used for scanning.

8 Data management

An electronic CRF (eCRF) will be completed by the Investigator and/or his/her delegate.

All patients who sign the informed consent will be archived. A minimum set of information is required for patients who are screened but not randomized: date of signed informed consent, demographics, assessment of inclusion/exclusion criteria where applicable, primary reason for non-continuation, adverse events, and any concomitant medications.

Front-end change checks will be performed at the time of data collection, and back-end change checks will be used by the Data Manager to check for discrepancies and ensure data consistency and completeness.

Administrative practices and data management

Medical record forms (CRFs) must be completed at the time of data collection. The complete CRF memory device containing the digitized clinical images should be attached to each patient's study file.

All data required for this study will be collected using paper-based CRFs. CRFs will be kept in a secure, locked location that will only be accessed by the Principal Investigator and the data collector. The data will also be accessible to the sponsor for monitoring and evaluation purposes at its discretion. After completion of the 1-week follow-up, copies of all CRFs will be sent to the investigator who will check the data and store them in a protected computer with a password known only to him. The data will be processed by an expert statistician. The patient's identity will be protected and known only to the study participants listed in this protocol.

Case Report Forms (CRFs)

- Patient informed consent form
- CRF Patient Eligibility
- CRF Rating
- Complications, protocol deviation and CRF drop-out

Changes and violations of the Protocol

Changes to this protocol may be necessary, and protocol violations are likely to occur. Any protocol violation should be reported in the "Complications, Protocol Deviation, and CRF Dropout" section. If you experience any problems, contact your studio monitor immediately.

Data Ownership

The data belongs to the sponsor.

Essential bibliography

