3. STUDY DESIGN

The present study is a 2-week double-arm randomized controlled trial.

The study will be carried out in the following ways:

- Randomization: Using a computer-generated, centralized random number with random codes (A, B) placed in sequentially numbered sealed opaque envelopes provided by the study consultant. A simple randomization procedure will be used.
- Concealment of assignment: Doctors involved in patient treatment will never know which mouthwash will be delivered to patients. Identical and indistinguishable bottles with mouthwash will be prepared by a person designated by the sponsor. The mouthwash will be poured into identical vials labeled with only one letter (A, B), and only the person designated by the sponsor will be of which product matches the letters. The random assignment will be made by opening the sequentially numbered sealed envelope just before the surgery.
- Blinded assessment: A single, independent, blinded assessor will perform all clinical measurements. Patients will not be aware of the mouthwash they will use. In addition, the operator evaluators and statistician will remain blinded until statistical analysis (blinded study) is performed. The codices (A, B) will be broken at the time of writing the manuscript.

The principles outlined in the Declaration of Helsinki on clinical research involving human subjects will be respected. Written informed consent will be obtained for each patient.

The study will be reported according to the CONSORT statement to improve the quality of reports of randomized parallel-group trials (<http://www.consort-statement.org/>).

A total of 3 visits will therefore be carried out:

- A screening/baseline visit will help establish patients' eligibility for inclusion in the study, followed by baseline data recording and first supervised mouthwash application
- A 1-week experimental visit
- A 2-week experimental visit and end of study

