4.4 Study program

Screening and baseline visit (V1)

Potentially eligible patients are screened to determine their eligibility for the study. Complete (Patient Eligibility CRF) and record the number and reason for patients not included.

Prior to enrollment, all patients will be asked to sign an informed consent form to document that they understand the purpose of the study (including procedures, follow-up assessments, and any potential risks involved), have been given the opportunity to ask questions related to this study, and have been informed of treatment alternatives.

At the recruitment visit, the clinician should assess the presence of an oral ulcer, rule out lesions of neoplastic, infectious, or allergic origin, and remove, if present, any causative agents (such as sharp edges of teeth, fillings, crowns, dentures, or braces).

Primary Results:

- Pain intensity. It is measured using the VAS consisting of a 10 cm line [13], where 0 indicates no pain and 10 indicates severe pain.
- Size of each ulcer. A sheet of clear plastic will be applied directly to the ulcer and using a permanent waterproof marker the circumference of the ulcer will be traced and then placed on a graph paper and the number of mm² units included within the drawn area will be counted.

Secondary Results:

- Thermography
- Ulcer Severity Score (USS)

Treatment will be started on the same day with strict infection control measures.

The assessor will open the sequentially sealed envelope corresponding to the patient's recruitment number and write on the CRF the progressive number of the patient contained in the envelope and to which group (A or B) the patient will be assigned.

Patients will receive three anonymous bottles, coded with A, B containing the mouthwash and a scoop. Patients will apply mouthwash. This procedure will be performed under the supervision of the outcome measure which will provide further explanations to patients if necessary.

Participants will be asked to flush with 10mL of mouthwash twice daily ~~directly onto the ulcer~~. Patients were prevented from eating, drinking, or rinsing their mouths for at least one hour after each application.

Observation at 1 week (V2) and at 2 weeks (V3):

- Pain intensity using the VAS scale. The following outcome measures will be recorded by the blinded outcome assessor:
- Size of each ulcer using a clear plastic sheet
- Thermography/ Ulcer severity score (USS)

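### Sections 4.4 and 6.1 call ulcer size primary, section 7.3 gives a primary test to VAS pain only, and no rule says which decides success

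*Combined protocol and SAP*

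**What the plan says.** - **Section 4.4** lists pain intensity on the VAS and ulcer size under its primary heading, without ranking: "Size of each ulcer. A sheet of clear plastic will be applied directly to the ulcer". Thermography and the Ulcer Severity Score (USS) are listed as secondary.
- **Section 6.1** repeats both outcomes as primary objectives: "Size of each ulcer. A sheet of transparent plastic will be applied directly to the ulcer". The section headed "6.2 Evaluation of secondary objectives" again holds only thermography and USS as efficacy outcomes.
- **Section 7.2** defines the per-protocol population by the availability of primary outcomes, in the plural.
- **Section 7.3** gives one primary hypothesis, for VAS alone: "This primary efficacy analysis will be performed on ITT, using the null hypothesis of no between-group difference in overall VAS change from baseline". It is evaluated at Day 7 with baseline VAS as covariate. The other efficacy analysis reads: "For secondary quantitative efficacy variables, cross-treatment group comparison of change from baseline will be done by the same ANOVA model". The section ends: "All statistical comparisons will be conducted at the significance level 0.05".
- **Section 2** puts pain, ulcer area, thermography and USS into one null hypothesis at 14 days.
- **Section 7.1** sizes the trial "to detect a significant difference in means of 0.820 assuming the common standard deviation is 1.80", without naming the outcome or the visit.
- **Section 3 (Study design)**: "The codices (A, B) will be broken at the time of writing the manuscript".

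**The concern.** Ulcer size carries the primary label twice, yet the analysis section has no primary test for it and does not call it secondary. No section says whether success rests on VAS alone, on either declared primary, or on both.

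The choice matters most when VAS is not significant and ulcer size is. Sections 4.4 and 6.1 would then support reporting a positive primary outcome, and section 7.3 would not. The plan contains nothing that fixes the answer before the results and the codes are known.

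**Working it through.** **1. Can the text settle it?** Three readings are possible.
- VAS alone decides. Section 7.3 points this way, but sections 4.4 and 6.1 contradict it, and the plural in section 7.2 does not fit.
- Either primary suffices. The two labels and the common 0.05 level allow it, but no section says it.
- Both are required. The labels allow this too, but no section says it.

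Section 2 does not decide between them, because it joins all four outcomes and uses a different day from section 7.3. Section 7.1 does not decide either, because it names no outcome.

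**2. Error rate under each reading** (two-sided 5% per test, no true effect; correlations are assumptions, since the documents give none).
- VAS alone: 0.05.
- Either suffices, independent: 1 − 0.95² = 0.0975. From the bivariate normal: 0.0907 at correlation 0.5 and 0.0781 at 0.8.
- In the product's favour only, independent: 1 − 0.975² = 0.049, against 0.025 for VAS alone.
- Both required: no inflation.

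**3. How often the sections would disagree** (VAS not significant, ulcer size significant).
- No true effect, P(either) − 0.05: 0.0475, 0.0407 and 0.0281 at correlations 0, 0.5 and 0.8.
- True effects, P(ulcer size) − P(both), with assumed power of 80% each: 0.80 − 0.64 = 0.16 if independent, 0.80 − 0.687 = 0.113 at correlation 0.5.
- The same with 40% each: 0.40 − 0.16 = 0.24, and 0.40 − 0.239 = 0.161.

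The subtracted terms are also the joint power if both outcomes were required: 64% or 69%, and 16% or 24%.

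**4. VAS power, needed to cost a VAS-first rule.** Inputs from section 7.1: difference 0.82, SD 1.80, 29 per group. That these refer to VAS is an assumption.
- Unadjusted t test: noncentrality 0.82 / (1.80 × √(2/29)) = 1.735, 56 df, critical value 2.003, power 0.399. The stated 80% is therefore not reproduced. That is a separate matter and does not bear on which outcome governs.
- With the baseline covariate of section 7.3: residual SD = 1.80 × √(1 − r²), 55 df, critical value 2.004.

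| Assumed baseline correlation r | Residual SD | Noncentrality | Power at 5% | VAS not significant | Power at 2.5% |
|---|---|---|---|---|---|
| 0.3 | 1.717 | 1.818 | 0.431 | 57% | 0.321 |
| 0.5 | 1.559 | 2.003 | 0.503 | 50% | 0.388 |
| 0.7 | 1.285 | 2.429 | 0.665 | 33% | 0.553 |

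If 1.80 is instead the SD of change, the residual SD is 1.80 × √((1 + r)/2) and power is 0.561, 0.503 and 0.456, inside the same range.

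**5. Fixed sequence against Holm.** Holm declares VAS significant if its p-value is at most 0.025, or at most 0.05 when the ulcer-area p-value is at most 0.025. VAS power under Holm therefore lies between the last column and the 5% column of the table.

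For ulcer area, take an assumed 80% power at 5%, which means a noncentrality of 1.96 + 0.84 = 2.80.
- Holm: at least Φ(2.80 − 2.24) = Φ(0.56) = 0.71.
- Fixed sequence, independent outcomes: 0.80 × 0.431 = 0.34 up to 0.80 × 0.665 = 0.53.

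**The case against.** The strongest reply is that section 7.3 governs. It alone states a hypothesis, model, day and significance level, and it names a single primary analysis. On that reading the error rate is 5% and the defect is a wrong label in sections 4.4 and 6.1. This is the most natural reading, and it limits the point: 9.75% is not the error rate of the plan as written. A reader might infer that it is, but no section says that either outcome suffices. It does not dispose of the point, because no text ranks section 7.3 above the others or makes ulcer size secondary.

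A reader might also infer that the more favourable section could be picked from the coded p-values alone, without the codes. The documents do not support that for a positive claim. A two-sided A-versus-B p-value does not show whether the product or the placebo did better, and section 3 keeps the codes until the manuscript is written. What remains is that results and codes are both known at that stage, and the success rule is still open.

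The doubt does not extend to thermography and USS, which sections 4.4 and 6.2 plainly label secondary.

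Finally, fixed sequence or Holm is a design preference. That is fair: any single rule stated in advance would remove the contradiction.

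**Conclusion.** The contradiction is real and leaves the trial's primary conclusion open in one identifiable case: VAS not significant, ulcer size significant. Its size depends on the reading. If section 7.3 governs, there is no inflation, only a labelling error. If either outcome can be claimed, the two-sided error rate rises from 5% to between 7.8% and 9.75% for assumed correlations from 0.8 down to 0, about half of it favouring the product. With real effects, the disputed case would arise in about 11% to 24% of trials at the assumed powers and correlations.

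This should be corrected. It is not fatal, because a defensible 5% reading exists and amended text closes the gap. Confidence in the inconsistency itself is high, since it rests on the wording alone.

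**What to change.** Before any between-group comparison is run, including one by coded group A versus B, state one success rule and align sections 2, 4.4, 6.1, 7.2 and 7.3 with it. The choice is the sponsor's.

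- **Simplest, consistent with section 7.3:** VAS change is the single primary, on one day reconciled between sections 2 (14 days) and 7.3 (Day 7). Ulcer area is relabelled key secondary and tested at two-sided 5% only if VAS is significant.
- **If ulcer area is to be claimable on its own:** Holm across the two outcomes.

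Both options hold the error rate at or below 5%. Thermography and USS stay secondary.

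As a minor clarification in the same edit, the ulcer-area model should use baseline ulcer area as covariate. Read literally, the same model would carry baseline VAS. It also needs one ulcer-area value per patient, for example the total area of the ulcers present at baseline, because section 3.1 admits patients with more than one.

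**Cost:** text only, but a substantive amendment. Under the fixed sequence, ulcer area cannot be claimed when VAS is not significant. If the section 7.1 inputs refer to VAS, which is not stated, that would happen in about 57% to 33% of trials for baseline correlations of 0.3 to 0.7. Holm avoids this at the price of somewhat lower VAS power: for example, between 39% and 50%, instead of 50%, at a baseline correlation of 0.5.

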3. CRITERIA FOR THE SELECTION OF STUDY SUBJECTS

3.1 Inclusion Criteria

Patients must meet all of the following inclusion criteria to be eligible for study enrollment:

1. Patients with at least one well-defined ulcer
2. Any patient who is at least 18 years old and able to sign an informed consent.

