In the event of any complication observed during any of the scheduled visits or during an emergency visit, protocol deviation and drop out should be filled out CRF.

Unscheduled visits may be made during the study at the discretion of the Investigator. Relevant information will be collected in the CRF.

The study plan and the scheduled items are summarized in the following flowchart:

Visit	Screening and Baseline (V1)	1 week (V2)	2 week (V3)
	Day 0	Day 7	Day 14
Evaluation			
Inclusion and Exclusion Criteria	✓		
Informed consent	✓		
First mouthwash application	✓		
Pain Assessment (VAS)	✓	✓	✓
Ulcer measurement	✓	✓	✓
Thermography	✓	✓	✓
Ulcer severity Score (USS)	✓	✓	✓
Complications		✓	✓

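### The primary Day 7 VAS model is valid, but it leaves out baseline ulcer size, a measure already taken in every patient that could add precision at almost no cost

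*Combined protocol and SAP*

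**What the plan says.** Section 7.3 (Statistical analysis) sets the primary efficacy analysis on VAS in the ITT population. The parameter compared between the groups "is the mean change from baseline on Day 7 within the given product", at the two-sided 5% level. On the model it says: "This hypothesis will be tested with an Analysis of Variance (ANOVA) with baseline values of VAS as a covariate". Baseline VAS is the only covariate named. The PP repeat is the only robustness analysis, and under strong non-normality the test becomes an unadjusted Wilcoxon rank-sum test.

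Four other places bear on the point:

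- Section 3.1 (Inclusion Criteria) asks for "Patients with at least one well-defined ulcer" and gives no minimum or maximum size. Section 2 covers ulcers of either traumatic or aphthous origin.
- Section 3 (Study Design) specifies simple randomisation and no stratification.
- The flowchart in section 4.4 ticks the row "Ulcer measurement" at Day 0, Day 7 and Day 14. Section 6.1.1 also lists lesion measurement on Day 0, ahead of mouthwash application.
- Sections 4.4 and 6.1 list the size of each ulcer, in mm², as a primary result beside VAS.

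**The concern.** A larger ulcer may take longer to close, and so may still hurt at Day 7 by more than its baseline pain would predict. That is plausible but is an assumption: the documents neither state nor quantify it. If it is true, leaving size out has two consequences. Variation that could be explained stays in the error term, which widens the confidence interval. A chance difference in ulcer size between two small arms, which simple randomisation does nothing to limit, also carries over into the estimated pain difference of this one trial. The plan would forgo that precision although it already collects the measurement.

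**Working it through.** **Inputs from the documents.** Difference 0.820, SD 1.80, 29 per arm for 80% power and 30 per arm enrolled (section 7.1); two-sided 5% (section 7.3).

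**Inputs assumed.** The partial correlation r between baseline size and Day 7 VAS given baseline VAS is not in the documents; a range is used. Section 7.1 writes "assuming the common standard deviation is 1.80 using a two-group t Student test" and does not say whether 1.80 is the SD of raw VAS, of change, or the residual SD after baseline adjustment. It is first taken as the residual SD.

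**Step 1: the plan's own figure.** Section 7.1 states: "A sample size of 29 subjects for each group (power 80%) to detect a significant difference in means of 0.820". The two-group formula gives

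n = 2 × (1.96 + 0.842)² × 1.80² / 0.820² = 75.6, so 76 per arm (77 with the t distribution).

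The stated 29 is not reproduced. At 29 per arm the power is 39.9% (noncentral t, two-sided). The dropout step does reproduce: 29 / 0.97 = 29.9, so 30.

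**Step 2: gain in precision.** Adding size multiplies the residual variance by (1 − r²), so the residual SD is 1.80 × √(1 − r²). Power is from the noncentral t at 29 per arm, with one further degree of freedom deducted.

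| r | Variance removed (r²) | Residual SD | Power at 29 per arm | n per arm for 80% |
|---|---|---|---|---|
| 0 | 0% | 1.800 | 39.9% | 77 |
| 0.1 | 1% | 1.791 | 40.2% | 76 |
| 0.2 | 4% | 1.764 | 41.3% | 74 |
| 0.3 | 9% | 1.717 | 43.1% | 70 |
| 0.4 | 16% | 1.650 | 46.0% | 65 |
| 0.5 | 25% | 1.559 | 50.3% | 58 |

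The gain can also be read apart from the sample-size problem. If the design truly had 80% power at 29 per arm, adding size would give 80.4%, 81.6%, 83.5% and 89.9% at r = 0.1, 0.2, 0.3 and 0.5. At r = 0 the lost degree of freedom has no visible effect.

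**Step 3: chance imbalance.** With 30 per arm (taken as equal), the difference between arms in a standardised baseline variable has SD √(2/30) = 0.258. Its median absolute value is 0.674 × 0.258 = 0.174, and its 95% limit is 1.96 × 0.258 = 0.506. The variable that matters here is the part of size not explained by baseline VAS. Shift in the pain difference = r × 1.80 × imbalance.

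| r | Shift at median imbalance | Shift at 95% limit |
|---|---|---|
| 0.2 | 0.06 | 0.18 |
| 0.3 | 0.09 | 0.27 |
| 0.5 | 0.16 | 0.46 |

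Against 0.820, for r = 0.2 to 0.5, that is 8% to 19% at the median imbalance and 22% to 56% at the 95% limit.

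**Step 4: if 1.80 is the unadjusted SD.** Assume, for illustration, a correlation of 0.5 between baseline and Day 7 VAS. The residual SD is then 1.80 × √0.75 = 1.56. The 95%-limit shifts fall to 0.2 × 1.56 × 0.506 = 0.16, 0.3 × 1.56 × 0.506 = 0.24 and 0.5 × 1.56 × 0.506 = 0.39 points.

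**The case against.** The planned model already adjusts for the baseline of the outcome. Under randomisation it is unbiased on average and keeps its type I error, and its confidence interval already allows for chance imbalance in variables left out. A reader might infer that omitting ulcer size makes the primary analysis biased or wrong. The documents do not support that, and this part of the objection stands in full.

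A reader might also take a third to a half of the planned difference as the likely distortion. That needs r of 0.3 to 0.5 together with an imbalance at the 95% limit. At the median imbalance the shift is at most 0.16 points over the range examined. If size and baseline pain are correlated, the VAS covariate also absorbs part of any raw imbalance in size.

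The value of r is unknown, and at 0.2 or below the gain is small: 1.4 percentage points of power at r = 0.2. This stands too. It limits the benefit but does not turn it into a loss, because the price at r = 0 is one degree of freedom.

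Finally, size is recorded per ulcer and no patient-level summary is defined. Total area, the largest ulcer or an index ulcer could each be argued for. So the change needs a definition as well as a covariate name.

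**Conclusion.** The point holds as an inexpensive gain in precision, not as an error in the plan. The facts are clear from the documents: baseline VAS is the only covariate, ulcer size is measured in everyone on Day 0, entry does not restrict size, and allocation is simple. The size of the benefit rests on the assumed r and on how 1.80 is read. It is modest at r of 0.2 or less and useful at about 0.4 or more.

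Two limits apply. The gain is lost if the unadjusted Wilcoxon fallback is used, which drops baseline VAS as well. Nor does adding size rescue the sample size: even at r = 0.5 power is only about 50% on the plan's own inputs. If 1.80 is the unadjusted SD, covariates would have to explain about 63% of the variance for 29 per arm to give 80% power. The mismatch in section 7.1 needs its own correction.

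**What to change.** In section 7.3, before unblinding, prespecify the primary Day 7 VAS model as treatment + baseline VAS + one patient-level measure of baseline ulcer size, and use the same terms in the PP analysis. Define that measure in the text, for example the total area of all ulcers at Day 0 on the square-root scale. The choice of summary and scale matters less than fixing it in advance, since an adjustment added after an imbalance has been seen would be post hoc.

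The cost is one degree of freedom (at 29 per arm, residual degrees of freedom go from 58 − 3 = 55 to 58 − 4 = 54), one definition and one line of text. No new data are needed.
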